3.1 Primary estimand

The primary estimand for the study is: In adults with no more than a mild to moderate high-frequency hearing loss and who undergo drilling during skull-based surgery, what is the difference in the proportion of patients experiencing PTS in the contralateral ear (the proportion of PTS-positive subjects defined as the ratio of PTS-positive subjects (defined as all subjects who in audiogram are identified as having a PTS of > 10 dB HL increase at any frequency between 2-6 kHz post-surgery as compared to baseline audiogram) to total number of subjects in each study arm/group) between ZNS treatment compared to Placebo, 30 days (+/- 3 days) after randomization or death (whichever occurs first).

3.2 Primary Efficacy Outcome

The study is designed to test the null hypothesis associated with the primary efficacy measure. The primary efficacy outcome will be the proportion of PTS-positive subjects defined as the ratio of PTS-positive subjects to total number of subjects in each study arm/group. PTS positive will be defined as all subjects who in audiogram are identified as having a permanent threshold shift (PTS) of $\geq 10 \, \text{db}$ HL increase at any frequency between 2-6 kHz post-surgery as compared to baseline audiogram. A SAS code will be written to code all the patients for whom the difference at any frequency from 2-6 kHz in hearing thresholds (30 days (+/-3 days) post-surgery - Baseline) is $\geq 10 \, \text{db}$ HL as PTS-positive. If this difference will be less than 10dB then the patients will be coded as non-PTS positive.

For the primary outcome measure, the null and alternative hypotheses for each pairwise comparison are provided below.

3.2.1 Comparison of the proportion of PTS-positive patients between ZNS pre-op and Placebo

$$H_0: p_{ZNS_{pre-op}} - p_{Placebo} = 0$$
 $H_A: p_{ZNS_{pre-op}} < p_{Placebo}$

We hypothesize that ZNS pre-op will reduce the proportion of PTS-positive patients by an absolute difference of 25% as compared to placebo

3.2.2 Comparison of the proportion of PTS-positive patients between ZNS post-op and Placebo

$$H_0: p_{ZNS_{post-op}} - p_{Placebo} = 0$$
 $H_A: p_{ZNS_{post-op}} < p_{Placebo}$

We hypothesize that ZNS post-op will reduce the proportion of PTS-positive patients by an absolute difference of 25% as compared to placebo. Our one-sided hypothesis is supported by animal studies, and lack of any evidence of hearing loss as a side effect of ZNS in human studies. The statistical testing will be performed using Bonferroni method to control for type I error rate at one-sided alpha level of 0.0125.

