2.3 Study Population

We plan to enroll approximately 234 subjects over approximately 4 years. Subjects will be randomized in a balanced fashion into one of the 3 arms: ZNS 100 mg pre-op, Placebo, or ZNS 100 mg post-op. We proposed the three-group design in order to establish a common control group between the experimental groups. Enrolled study subjects will be randomized into three equal groups. The placebo group is the common group for comparison to each active group independently. Alpha error will be adjusted for multiple comparison.

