2.7 Sample Size Determination for The Primary Efficacy Outcome Measure

The primary efficacy outcome will be the proportion of PTS positive subjects defined as the ratio of PTS-positive subjects to total number of subjects in each study arm/group. Using pilot data from a retrospective chart review of 75 similar patients undergoing \geq 1-hour drill noise exposure, we estimate the proportion of PTS positive subjects in the placebo group will be 50%. We hypothesize that the expected effect of ZNS either pre-op or post-op will be a 50% reduction of the proportion of subjects with PTS positive as compared to placebo group. This is the desired clinically significant effect for treating hearing loss for single dose of 100 mg ZNS.

The sample size for this study was calculated for the planned comparisons of each of the ZNS groups with the placebo group using a balanced design and a one-sided alpha level of 0.0125 Based on the data from our retrospective study, using Fisher's exact test we estimated that 78 subjects in the ZNS group and 78 subjects in the placebo group will be needed to provide us with 80.4 % power to detect a 50% reduction in the proportion of PTS positive subjects *(from 50% to*

^{**}Dispensed on the day of surgery with instruction to take first dose prior to surgery and second dose after surgery.

^{***} Plasma sample for PGx will be collected at baseline visit. Plasma sample for ZNS level and PGx, electrolyte panel, BUN, Cr, ALT, and AST will be collected 12 hours after first dose.

25% corresponding to an absolute proportion difference of 25%) at the 1-sided alpha level of 0.0125 for each ZNS-Placebo group comparison. A total of 234 subjects will be enrolled to be randomized in this study. All efforts will be made minimize and eliminate drop outs. Given the short term-follow-up of study subjects in a period where they are under medical care, few, if any, drop-outs or lost to follow-up are expected.

Sample size calculations were carried out using PROC POWER procedure in SAS 9.4.

3 Study Outcomes

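### Fixed Bonferroni at 0.0125 for both ZNS comparisons gives up power that Holm's step-down would recover at the same family-wise error

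*SAP*

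**What the plan says.** The trial has three equal arms and two primary comparisons, pre-op ZNS v placebo and post-op ZNS v placebo, with a shared placebo group. SAP 2.3 says only "Alpha error will be adjusted for multiple comparison". SAP 3.2.2 names the method: "The statistical testing will be performed using Bonferroni method to control for type I error rate at one-sided alpha level of 0.0125". SAP 2.7 makes clear that this level applies to each test: "at the 1-sided alpha level of 0.0125 for each ZNS-Placebo group comparison". Protocol 12.3 gives the same level.

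The sample size is set for one comparison at that level: "78 subjects in the ZNS group and 78 subjects in the placebo group will be needed to provide us with 80.4 % power". The same effect is expected in both arms. SAP 3.2.1 has "We hypothesize that ZNS pre-op will reduce the proportion of PTS-positive patients by an absolute difference of 25% as compared to placebo" and SAP 3.2.2 has "We hypothesize that ZNS post-op will reduce the proportion of PTS-positive patients by an absolute difference of 25% as compared to placebo".

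No step-down, Hochberg, Dunnett or gatekeeping rule for these two comparisons appears in either document.

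**The concern.** Under fixed Bonferroni the second comparison must reach 0.0125 even when the first has already succeeded. At that point only one null hypothesis remains in the family, and the full 0.025 could be spent on it without raising the family-wise error. The primary objective (Protocol 2.1, SAP 2.2.1) asks whether either or both schedules work, and the design assumes that both do. That is the situation in which fixed Bonferroni costs most.

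A concrete case: suppose placebo has 39 PTS-positive of 78. An arm with 24 of 78 has a one-sided Fisher p of 0.0110 and passes. An arm with 25 of 78 has p = 0.0170 and fails under Bonferroni, even if the other arm has already passed. Under Holm it would then succeed. At stake is the chance of showing that both schedules work; the trial's validity is not in question.

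**Working it through.** **Inputs.** From SAP 2.7: "we estimate the proportion of PTS positive subjects in the placebo group will be 50" per cent; ZNS 25%; 78 per arm; Fisher's exact test; one-sided 0.0125 per comparison. From SAP 3.2.1 and 3.2.2: the same 25-point difference in both arms. From SAP 9: one look at 26 per arm, with an arm stopped if z ≤ 0.6850, where z is the inverse-normal transform of the one-sided Fisher p. The family-wise level is not stated; I take it as 0.0125 + 0.0125 = 0.025.

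**Step 1: the plan's own power.** Arcsine approximation with continuity correction, n = 78:

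- d = arcsin√(0.50 − 1/156) − arcsin√(0.25 + 1/156) = 0.2480
- power = Φ(d√156 − 2.2414) = Φ(3.0977 − 2.2414) = Φ(0.8563) = 80.4%, the stated figure
- exact enumeration of Fisher's test gives 80.74%

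**Step 2: Bonferroni and Holm, exact.** Given the placebo count k, the two ZNS arms are independent. Let w(k) be the binomial probability of k. For arm j, let r_j be the probability of p ≤ 0.0125 given k, and s_j the probability of p ≤ 0.025 given k.

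- Bonferroni, arm 1: Σ w·r₁. Both arms: Σ w·r₁r₂.
- Holm, arm 1: Σ w·[r₁ + (s₁ − r₁)r₂]. Both arms: Σ w·[r₁r₂ + (s₁ − r₁)r₂ + (s₂ − r₂)r₁].
- At least one: Σ w·[r₁ + r₂ − r₁r₂] under either method, because Holm's first step is the Bonferroni test.

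**Step 3: the futility rule.** The calculation is repeated with the counts split into 26 and 52 per arm. An arm with interim z ≤ 0.6850 counts as not rejected. Exact enumeration agrees with 2,000,000 simulated trials to within 0.1 point.

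| Scenario (placebo 50%) | Quantity | Bonferroni | Holm |
|---|---|---|---|
| Both arms 25%, no interim | given arm | 80.7% | 85.3% |
| | both arms | 70.2% | 79.3% |
| | at least one | 91.3% | 91.3% |
| Both arms 25%, futility rule | given arm | 71.1% | 73.8% |
| | both arms | 57.4% | 62.8% |
| | at least one | 84.8% | 84.8% |
| Arms 25% and 30%, no interim | 25% arm | 80.7% | 83.0% |
| | 30% arm | 57.6% | 65.2% |
| | both arms | 52.6% | 62.5% |
| Arms 25% and 50%, no interim | effective arm | 80.7% | 80.7% |
| | false rejection of the other | 1.00% | 1.53% |
| Both arms 50%, no interim | any false rejection | 1.87% | 1.87% |

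**Step 4: consistency.** The extra both-arm wins under Holm are 79.28 − 70.18 = 9.10 points, shared equally between the arms: 80.74 + 9.10/2 = 85.29%. Also 2 × 80.74 − 70.18 = 91.3%. The false-rejection rates stay below 2.5%.

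**Step 5: the gain in patients.** With no interim, fixed Bonferroni needs 87 per arm to match Holm's 85.3% for a given arm, or 91 per arm to match its both-arm power (79.8% v 79.3%). That is 3 × 9 = 27 or 3 × 13 = 39 more subjects than 234.

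**The case against.** The strongest reply is that nothing is broken. Bonferroni is valid and stated in advance, and the sample size was built on it. No stated power target is missed because of it. SAP 2.3 describes each active group as compared with placebo independently, and a sponsor may prefer that one arm's verdict not depend on the other's. The only trial-level power statement (Protocol 12.4, SAP 9) concerns success on one or both comparisons, where Holm gains nothing. Neither document sets a target for winning both. All of this stands. It limits the point to an improvement, but it does not give a reason to leave the alpha unused.

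The no-interim figures also flatter the gain. With the futility rule it is 2.7 points for a given arm and 5.4 points for both, about 60% of the no-interim gains of 4.6 and 9.1. The smaller figures describe the trial as planned.

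The change also touches more than one line. The bound 0.6850 is tied to the final level of 0.0125. Under the current trend at one-third information, conditional power at the bound is Φ((0.685/√(1/3) − 2.2414)/√(2/3)) = 9.8%. Replacing 2.2414 by 1.9600 gives 17.2%, and a 10% bound would be about 0.53. Keeping 0.6850 does not harm error control, but its stated rationale would then hold only for an arm tested at 0.0125. The Newcombe intervals in SAP 7.1.1 sit more naturally beside fixed-level tests. These are matters of drafting and do not defeat the proposal.

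Finally, 0.025 is inferred. SAP 3.2.2 read alone could make 0.0125 the level for the whole family, but SAP 2.7 assigns 0.0125 to each comparison.

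**Conclusion.** The concern holds as a recommended improvement. Holm is never less powerful than the planned procedure, keeps the same inferred family-wise level, and needs no assumption about the correlation induced by the shared placebo arm.

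The size of the gain depends on both schedules working. It is largest for a both-arms conclusion, is smaller once the futility rule applies, and disappears if only one arm is effective. The figures assume 50% on placebo, 78 analysed per arm and, for the main scenario, the full 25-point effect in both arms. The futility figures also treat the stopping rule as always followed.

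Buying the same power by enrolment looks unrealistic. Protocol 12.4 and SAP 4.4 count about 50 surgeries a year with at least an hour of drilling, so about 200 in four years against 234 needed. That count predates the 45-minute criterion, so the true pool may be larger.

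The 79.6% overall power stated in SAP 9 was not matched by any of the futility results above. That is a separate matter and does not affect this conclusion.

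**What to change.** In SAP 3.2 and 7.1.1, replace the fixed-level rule with Holm: order the two one-sided p-values, test the smaller at 0.0125 and, only if it is significant, test the other at 0.025. State the family-wise one-sided level of 0.025 explicitly. Add that an arm stopped for futility counts as not rejected, so the remaining arm is tested at 0.0125.

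Three consequential edits:

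- Align Protocol 12.3 and 12.4, which carry the 0.0125 level.
- In SAP 9, keep 0.6850 and say that its conditional power refers to a final level of 0.0125. The success event described there, one or both comparisons at 0.0125, is unchanged under Holm.
- In SAP 7.1.1, state the interval level. Intervals can stay at the Bonferroni level, with a note that an arm rejected at Holm's second step may have an interval that includes zero.

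The change must be fixed before any unblinded comparison is seen. It needs no extra patients, data or visits. The cost is a few sentences and the loss of an exact match between intervals and tests.

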3.3 Secondary efficacy outcomes

The secondary outcome measures are key audiological and clinical assessments of hearing loss as listed below as continuous level variables.

- DPOAE: Distortion product otoacoustic emissions will be measured at baseline (before surgery), as well as within 8 hours and at 30 days (+/- 3 days) post-surgery to measure both temporary and permanent change in DPOAE amplitude relative to baseline. A change is noted in DPOAE amplitude at any frequency that is significantly greater than the stability of each measurement (i.e., 95% confidence interval of each measurement do not overlap).
- ECochG: Electrocochleography will be measured at baseline (before surgery) and at 30 days (+/- 3 days) post-surgery to measure change in ECochG AP amplitude, latency, and width.
- WIN testing: The Words in Noise Test will be administered at baseline (before surgery) and at 30 days (+/- 3 days) after surgery. The respective scores will be converted to Z-scores to evaluate any change in scores relative to baseline.

The study will also include an exploratory analysis aiming to identify biomarkers of response to ZNS.

3.4 Safety measures

AE and SAE that are temporally related to the intervention (beginning at time of dose through post-dose) will be evaluated for regulatory reportability as per FDA and IRB requirements. The PI and study team will review data in real time for safety. We will closely monitor and report all AE and SAE in the study per requirement.

Potential known side effects from the administration of ZNS:

- Somnolence
- Anorexia
- Dizziness
- Ataxia
- Agitation/irritability
- Difficulty with memory and/or concentration

ZNS may cause serious side effects including:

- Serious skin rash that can cause death.
- Serious allergic reactions that may affect different parts of the body.
- Less sweating and increase in body temperature (fever).
- Suicidal thoughts or actions in some people.
- Increased level of acid in blood (metabolic acidosis).
- Problems with concentration, attention, memory, thinking, speech, or language.

4 Analysis Populations

4.1 Target population

Target population includes all patients that meet the inclusion/exclusion criteria as defined in the study protocol.

4.2 Intent-to-treat (ITT) sample

ITT sample will include all subjects who are randomized. Following principles of intent-to-treat analysis all subjects will be analyzed in the treatment group they were randomized to when they were enrolled in the study.

4.3 The safety sample

The safety sample will include subjects from the full analysis population who will be enrolled and will receive active or placebo ZNS. Adherence to protocol does not affect inclusion in safety population. subjects are evaluated from the time of dose administration through two weeks post dose for drug related adverse events.

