## 8.0 REGULATORY AND REPORTING REQUIREMENTS

The entities providing oversight of safety and compliance with the protocol require reporting as outline below. Please refer to Appendix A for definitions and Appendix B for a grid of reporting timelines.

Adverse events will be tracked for the WU site from the time of dose administration through two weeks post dose and at the follow up 30 day visit for drug-related adverse events. All adverse events will be documented and assessed for relatedness to the study medication.

The study team will monitor for adverse events on an ongoing basis. Once the team becomes aware of an adverse event, the AE will be reported according to institutional guidelines. Reporting requirements for Washington University study team may be found in Section 8.1. Reporting requirements for secondary site study teams participating in Washington University-coordinated research may be found in Section 8.2.

In the event of a Serious Adverse Event determined by the PI to necessitate the breaking of the blind, the intervention assignment will be revealed by the independent programmer to the medical staff doctor caring for the patient. In the event the statistician is unable to be reached in a time needed, to assure the safety of the subject, the blind can be broken by [name] and information will be shared with the medical staff assuming care for the research subject.

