#### 11.1 Adverse Event Collection in the Case Report Forms

All adverse events that occur beginning with start of treatment must be captured in the AE Form.

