2.5 Treatment Assignment and Blinding

To ensure double-blinding of the trial, each subject will be randomized to one of three treatment arms via an interactive randomization tool (IRT) and assigned to a study group. Once randomized, each subject will be provided a kit on the day of surgery that contains two bottles, with one package labeled to be taken prior to surgery, and another package designated to be taken within 12 hours after surgery or when patient is released clinically to oral medication. For subjects randomized to "ZNS pre-op", the pre-op package will contain one ZNS capsule of 100 mg, and the post-op package will contain one placebo capsule that looks and tastes the same as ZNS capsules. For subjects randomized to "ZNS post-op", the pre-op package will contain one placebo capsule and the post-op package will contain one ZNS capsule of 100 mg. For the subjects randomized to "placebo", both pre- and post-op packages will contain capsules of placebo.

The study will be "masked" or "blinded" in the sense that all the study subjects and the study team members will be blinded to the assignment in the study groups. Only the pharmacist who will prepare the study drug kits and the unblinded Statistician will have access to the kit assignments. A copy of the randomization kit list with study ID assignments will be saved in a limited access folder on a secure network server at Pharm-Olam. The Medical Monitor will be contacted in emergent medical cases when knowing the treatments assignment is mandatory for clinical care of the patient.

At the time when we will need to "freeze" the data sets for purposes of developing the DSMB report, a series of SAS programs will be run from an independent programmer to produce data for each pairwise comparison into two subsets of data from the total cohort. Each subset will be de-identified. A previously prepared SAS code will be run in each subset and the output will be used to complete the table shells. Table shells will be blinded. If DSMB members find any safety issues, they may request specific unblinded data. The programmer preparing subsets will not be involved in the handling of data forms or the analysis of data. Table shells for DSMB (content and formats) will be agreed upon prior to start of study.

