5 GENERAL ASPECTS FOR STATISTICAL ANALYSES

5.1 General Methods

- All analyses and summaries will be produced using SAS® version 9.4 (or higher).
- Standard descriptive statistics will be used to describe distribution of demographic, clinical, and audiometric characteristics as well as outcome measures for all the study samples listed in section 4. For continuous level characteristics Q-Q plots and Shapiro-Wilk test will be used to test assumption of normality. If continuous level data is found to be normally distributed data, mean and standard deviation will be used as descriptive statistics, and if the assumption of normality is violated, we will report median and range for description of these variables. Frequency and relative frequency will be used for description of categorical level variables.
- The same number of decimal places as in the raw data will be presented when reporting range, 1 more decimal place than in the raw data will be presented when reporting the mean and median, and 2 more decimal places than in the raw data will be presented when reporting the standard deviation.
- Unless stated otherwise, tabular summaries will present columns for the active treatment arm ("ZNS pre-op" and "ZNS post-op"), placebo arm, and overall.
- Unless stated otherwise, the relative frequency will be based on the number of non-missing observations. The column header will still contain the number of subjects in the treatment group. There will be a row for the number of non-missing observations in the table (at each time point, if required) for each variable being summarized.
- Any calculated p-values will be presented to 3 decimal places; p-values less than 0.001 will be presented as 'p<0.001' and p-values greater than 0.999 will be presented as 'p>0.999'.
- All relevant subjects data will be included in listings and sorted by treatment group, subject ID, and visit, as applicable, for all randomized subjects.
- Unscheduled or repeat assessments will not be included in summary tables unless specified. All assessments will be included in the subject listings.
- All tables, listings and figures will include footers that identify the name of the program that created the output, together with the date and time on which it was created. Headers will include the total number of pages that the presentation contains and, for each page, the number of the page within the presentation.

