8.1.1 Safety monitoring

Adverse events will be tracked for the WU site from the time of dose administration through two weeks post dose for drug related adverse events Laboratory testing (electrolyte panel, BUN, Cr, ALT, and AST) done as part of the study conducted at WU site, will be collected post dose within 12 hours. In the event the lab values are not within normal limits post dose, the PI will be notified and recommend that the subjects be evaluated by his/her treating physician. Study subjects will remain in the study and lab tests repeated until within normal limits. All adverse events will be documented and assessed for relatedness to the study medication.

The study team will monitor for adverse events on an ongoing basis. Once the team becomes aware of an adverse event, the AE will be reported according to institutional guidelines. Reporting requirements for Washington University study team may be found in Section 1.1 of protocol. Reporting requirements for secondary site study teams participating in Washington University-coordinated research may be found in Section 1.2 of protocol.

Early stopping rule related to serious adverse events: In the event of a serious adverse event, DSMB will evaluate the association of the serious adverse events with the study arm, break the blind if needed, and if found to be associated with treatment, DSMB will consider the study for revision or stopping.

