12.2 Index of Proposed Listings

Listing Number	Listing Title	Sample Set
Listing 16.1.1	Subject Enrollment and Disposition All Subjects	All Subjects
Listing 16.1.2.1	Subject Inclusion and Exclusion Criteria	All Subjects
Listing 16.1.2.2	Protocol Deviations	All Subjects
Listing 16.1.3	Demographic Characteristics	All Subjects
Listing 16.1.4	Medical and Surgical History	Safety Sample Set
Listing 16.1.5	Hearing History and Occupation Exposure	Safety Sample Set
Listing 16.1.6	Concomitant Medications	Safety Sample Set
Listing 16.1.7	Study Drug Administration	Safety Sample Set
Listing 16.2.1	Audiogram Results on Hearing Thresholds	ITT Sample Set
Listing 16.2.2	Distortion Product Otoacoustic Emissions (DPOAE) Results	ITT Sample Set
Listing 16.2.3	Electrocochleography (ECochG) Results ITT Analysis Set	ITT Sample Set
Listing 16.2.4	Word in Noise (WIN) Test Results ITT Analysis Set	ITT Sample Set
Listing 16.2.5	LENS-Q Adapted for Surgical Noise Study Results at Screening ITT Analysis Set	ITT Sample Set
Listing 16.3.1.1	Serious Adverse Events	Safety Sample Set
Listing 16.3.1.2	Adverse Events Resulting in Death	Safety Sample Set
Listing 16.3.1.3	Treatment-emergent Adverse Events	Safety Sample Set
Listing 16.3.1.4	Treatment-emergent Adverse Events leading to Study Drug Interruption	Safety Sample Set
Listing 16.3.1.5	Treatment-emergent Adverse Events leading to Study Drug Withdrawn	Safety Sample Set

Listing Number	Listing Title	Sample Set
Listing 16.3.2.1	Clinical Laboratory Results at Screening: Biochemistry	Safety Sample Set
Listing 16.3.2.2	Pregnancy Test at Screening	Safety Sample Set
Listing 16.3.3	Physical Examination of Ears at Screening	Safety Sample Set

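### Adverse events in the post-op arm before its only zonisamide capsule are counted in the ZNS post-op column, because the SAP neither defines treatment-emergent nor splits events at capsule 2.

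*SAP*

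**What the plan says.** **Start of counting.** Protocol 11.1: "All adverse events that occur beginning with start of treatment must be captured in the AE Form". The calendars (Protocol 9.0, SAP 2.6) schedule AE assessment at surgery, within 12 hours afterwards, and at 30 days. Other sections name no particular dose. SAP 4.3: "subjects are evaluated from the time of dose administration through two weeks post dose for drug related adverse events". Protocol 8.0 tracks events "from the time of dose administration through two weeks post dose and at the follow up 30 day visit for drug-related adverse events".

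**What the post-op arm takes.** SAP 2.5: "the pre-op package will contain one placebo capsule and the post-op package will contain one ZNS capsule of 100 mg". The second capsule is due within 12 hours after surgery or on clinical release to oral medication.

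**Who is counted, and where.** SAP 4.3: "The safety sample will include subjects from the full analysis population who will be enrolled and will receive active or placebo ZNS". The same section says that adherence does not affect inclusion. SAP 5.1: "tabular summaries will present columns for the active treatment arm" (ZNS pre-op and ZNS post-op), plus placebo and overall. SAP 8 summarises all AEs and SAEs descriptively.

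**What is absent.** SAP 12.1 and 12.2 list treatment-emergent tables and listings, including Listing 16.3.1.5, "Treatment-emergent Adverse Events leading to Study Drug Withdrawn". Neither document defines treatment-emergent, ties AE onset to the active capsule, or separates events before capsule 2 from events after it.

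**The concern.** The calendar window is the same in all three arms, but its relation to ZNS is not. In the pre-op arm every event in the window follows ZNS. In the post-op arm the operation, the anaesthetic and recovery up to capsule 2 fall inside the window before any ZNS; until then that arm has had the same treatment as placebo.

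Two things are at stake. First, the ZNS post-op column mixes events that ZNS could have caused with events that it could not. That raises the column's absolute rate and pulls its contrast with placebo towards no difference, which is the unhelpful direction for a harm summary. Second, the tables of events leading to withdrawal of study drug set unlike things side by side in the two ZNS columns.

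**Working it through.** The plan states no figure on this point. Its power calculation concerns permanent threshold shift and is not used here.

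**Step 1. Order of events, from the documents**

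| Arm | Capsule 1 | Surgery and early recovery | Capsule 2 |
|---|---|---|---|
| ZNS pre-op | ZNS | after ZNS | placebo |
| ZNS post-op | placebo | before any ZNS | ZNS |
| Placebo | placebo | no ZNS | placebo |

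With counting from capsule 1, the surgery-visit AE assessment always precedes ZNS in the post-op arm, and the 12-hour assessment may do so.

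**Step 2. Withdrawal table and listing (no rates needed)**

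Study drug is two capsules. An event that leads to its withdrawal can only stop capsule 2, so it occurs before capsule 2. In the post-op arm all such events precede ZNS; in the pre-op arm all follow it.

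**Step 3. Share of the post-op column's events that precede ZNS**

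Assumptions: 4 to 8 h from capsule 1 to the end of surgery (not in the documents), plus the full 12 h to capsule 2. The gap g is then 16 to 20 h. The window is 14 × 24 = 336 h from capsule 1. The peri-operative AE rate is r times the later rate.

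Share = g·r / (g·r + 336 − g)

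| r | g = 16 h | g = 20 h |
|---|---|---|
| 1 | 16/336 = 4.8% | 20/336 = 6.0% |
| 3 | 48/368 = 13.0% | 60/376 = 16.0% |
| 5 | 80/400 = 20.0% | 100/416 = 24.0% |

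**Step 4. Attenuation of the subject-level contrast**

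Let b be the risk of an AE before capsule 2 (equal in the post-op and placebo arms), c the later risk on placebo and d the later risk on ZNS, with the two periods independent. The any-AE risks are 1 − (1 − b)(1 − c) and 1 − (1 − b)(1 − d), so the observed difference is (1 − b)(d − c).

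Assume c = 10% and d = 25%, a true difference of 15 points and a true risk ratio of 2.5. The same rate ratios fix b through b = 1 − exp[−r·g·0.1054/(336 − g)], where 0.1054 = −ln(0.90).

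- r = 1, g = 16: b = 1 − exp(−0.0053) = 0.5%. Risks 10.5% v 25.4%; difference 14.9 points; ratio 2.4.
- r = 5, g = 20: b = 1 − exp(−0.0333) = 3.3%. Risks 13.0% v 27.5%; difference 14.5 points; ratio 2.1.

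**Step 5. What a large attenuation would require**

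If b were 20%, 40% or 60%, the difference would be 0.8 × 15 = 12, 0.6 × 15 = 9 or 0.4 × 15 = 6 points. With c = 10%, the rate ratio implied by b is [−ln(1 − b)/0.1054] × (336 − g)/g. For b = 40% that is 4.85 × 15.8 = 77 (g = 20) to 4.85 × 20 = 97 (g = 16).

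**The case against.** The strongest reply is that placebo provides a concurrent control. It has the same window, the same operation and a placebo first capsule. A reader might infer that surgical events will make post-op ZNS look more harmful than placebo. The documents do not support that: the pre-ZNS events are expected equally in both columns. This part of the objection stands in full.

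A reader might also infer that a real harm signal would largely be lost. Step 5 shows what that needs: a peri-operative rate ratio far above 5. Such a ratio is possible after skull-base surgery, but the documents give no AE rates that would establish it. SAP 8 plans descriptive summaries and no AE test, so loss of power is not a defect of this plan. Nor is the use of only 78 placebo controls, since no peri-operative harm contrast is planned. The any-AE line is also the one most exposed to dilution. By preferred term, an event is diluted only by its own peri-operative background, although somnolence, dizziness and poor concentration could also follow anaesthesia. The table of related events is not a full answer, because relatedness is judged blind and no rule sets pre-ZNS events to unrelated.

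Two further strong readings fail:

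- **The serious-event rule ignores ZNS.** SAP 8.1.1 says "DSMB will evaluate the association of the serious adverse events with the study arm", but goes on to allow unblinding and makes association with treatment the condition for considering revision or stopping.
- **A post-op subject who misses capsule 2 stays in the ZNS column.** SAP 4.3 governs inclusion, not column. Only the ITT sample (SAP 4.2) is stated to be analysed as randomised; the safety sample is silent.

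Finally, counting from capsule 1 is the natural reading of Protocol 11.1 with the surgery-visit assessment, but Protocol 8.0, SAP 4.3 and SAP 8.1.1 do not name the dose. That is a reason to define the window.

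**Conclusion.** The point holds as a gap in the safety tabulation. Read from capsule 1, the post-op arm's AEs in surgery and early recovery are counted under ZNS post-op before any ZNS. That inflates the column's absolute rate and attenuates its subject-level contrast with placebo whenever the risk between the capsules is above zero. It creates no expected false excess.

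The documents do not allow the size to be fixed. Under the assumptions of steps 3 and 4, about 5% to 24% of the column's events precede ZNS, and a 15-point difference appears as 14.5 to 14.9 points. The loss is larger only if peri-operative AEs are much more frequent than that.

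The misalignment of Table 14.3.1.7 and Listing 16.3.1.5 needs no assumed rate; it follows from the two-capsule design. Overall this is a cheap improvement that should be made, not a threat to the trial's primary conclusion.

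**What to change.** In SAP 4.3, SAP 8 and the 14.3.1 tables:

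- Define treatment-emergent relative to each capsule, and state which dose opens and closes the AE window.
- Tabulate AEs and SAEs by onset before and after capsule 2 in all three arms. Before capsule 2, also show placebo and post-op combined as controls without ZNS.
- Show events leading to withdrawal by the capsule actually taken before the event.
- Give the DSMB the ZNS exposure at onset of each SAE, alongside arm.
- Keep the existing by-arm totals as an overview.
- Footnote, for every arm alike, how many subjects missed capsule 2; SAP 6.5 already summarises receipt of each dose. State, identically for all arms, where the first period ends for such subjects. Do not move only post-op non-takers to an unexposed group. Capsule 2 can depend on release to oral medication, so missing it may reflect a worse recovery, and reassigning one arm would select after randomisation.

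The cost is SAP wording and a few extra table columns. Capsule 1, surgery and capsule 2 can fall on one day, so the AE form needs onset time or a tick for before or after capsule 2, if it does not already collect this; the form is not in the documents. No extra visits or subjects are needed, and site staff stay blinded.
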